5.4 Strategies for Recruitment and Retention

Method of Subject Identification and Recruitment

NYU Langone Medical Center has an extensive recruitment base. Patients who are seen by medical staff at the NYU Langone Medical Center, who fit the eligibility criteria, will be referred for the study by the study PI, Co-I, and sub-investigators. If the patient is interested and agrees, then a member of the study staff will contact them. Once the patient is identified, study staff will meet with the patient or call them to provide additional information regarding study participation. After the patient has reviewed the consent form and asked all the questions, and provides consent to participate, the patient will be enrolled in the study.

Study Group Recruitment

Both Participants with neurological disorders and participants with MS and chronic pain will be recruited for participation in this study in two separate groups: 1) individuals with neurological disorders, 2) PwMS with Chronic Pain.

To clarify, participants with MS and chronic pain will be specifically recruited for study group 2 to evaluate any analgesic treatment effects. Participants with MS without chronic pain may still be eligible for study group 1, which has broader recruitment criteria and primarily aims to demonstrate feasibility of treatment across neurological disorders.

Advertisements

An IRB approved flyer will be posted in local physician offices and waiting rooms throughout NYU, the surrounding community. A description of the study will be posted on sites related to neurological disorder.

A flyer will be created for each study group to recruit for both participant pools.

Ripple

Participant personal information may be kept in Ripple™, a secure web application designed for the storing and management of personally identifying information of research participants. Ripple was initially developed at the University of Michigan to provide a user-friendly, web-based secure interface where research teams can centralize the storage and management of research participants' personal information, including name, participant ID, demographics, and study workflow (e.g., appointments). Participant information managed with ripple is private and secure. This information is kept in fully encrypted format inside dedicated databases that are segregated from other Ripple accounts and thus only authorized study staff will have access to the study data. Likewise, Ripple infrastructure complies with the privacy and security guidelines of the Health Insurance Portability and Accountability Act (HIPAA), including 2048-bit data encryption in transit and at rest, automatic logoff, audit trail, daily backups in triplicate dedicated servers, firewall, custom access permission for lab members, zxcvbn password strength estimation, and enterprise administrative safeguards to prevent unauthorized staff from accessing participant information. Furthermore, Ripple is used only for storing personally identifiable information of participants and is not used to capture other research data (e.g., questionnaires, health records, etc.). This ensures that the personally identifiable information and research data are segregated. Ripple is already being used at NYU Langone Health.

5.5 Duration of Study Participation

The study will be open for enrollment for three years from the date of enrollment commencement.

Participants may complete as many as twelve study visits over the course of the study and these visits may be completed within one year of consenting. The amount of study visits that a participant will be asked to complete will be at the study personnel's discretion. If the first VR session is determined to be the final session for that participant, all baseline study measures will be re-administered immediately following the VR session.

5.6 Total Number of Participants and Sites

Study Group 1 (Neurological Disorders): We will enroll a total of n=60 participants at a single site (NYU Ambulatory Care Center).

Study Group 2 (Chronic Pain in MS): We will enroll a total of n=44 PwMS and chronic pain at a single site (NYU Ambulatory Care Center)

CONFIDENTIAL

This material is the property of the NYU School of Medicine and Langone Medical Center. Do not disclose or use except as authorized in writing by the study sponsor

[figure not shown]
5.7 Participant Withdrawal or Termination

Participants may withdraw from the study at any point for any reason.

Should a participant feel any adverse event such as nausea at any point during the VR sessions, the headset will be removed and the session will be paused. The participant will be asked to rate their adverse event, nausea for this example, on a 1-10 likert scale, 1 being mild and 10 being the need to vomit. If the participant rates their nausea at a level of 7 or more or expresses the need to vomit the session will be ended for that day. If the participant rates the nausea below a 7 and expresses the desire to continue, then the study personnel will wait with the participant (for up to 5 minutes) until the nausea is resolved and will then resume the VR session. Should the participant experience nausea a second time in the same session then the headset will be removed and that day's VR session will be ended (see Figure 1).

The participant's participation in the study will be terminated if two VR sessions are cancelled due to nausea or if participants express the desire to stop.

Figure 1. Visual representation of study stop criteria

6 Study Device

6.1 Study Device Description

We will use the HTC Vive VR system running on a high performance desktop computer.

[figure not shown]
6.1.1 Administration of Device

Participants will be able to complete a maximum of twelve 1-hour sessions of virtual reality featuring two separate treatment catalogues of interactive experiences, games, or videos.

Figure 2: Painting on a Virtual Canvas

CONFIDENTIAL

This material is the property of the NYU School of Medicine and Langone Medical Center. Do not disclose or use except as authorized in writing by the study sponsor

A) The interactive catalogue includes a virtual 3D canvas that participants may paint upon, completion of daily tasks in a virtual kitchen, guided virtual meditation, interaction with music corresponding to the beats per minute of a song, virtual assessment of hand-eye coordination and range of motion among other experiences. See Figure 2 for an illustration of the virtual painting program.

B) The passive VR catalogue includes videos that are non-interactive and passively viewed. Participants may look in 360° at videos that include nature (i.e. underwater biomes, penguins and other animals, earthly biomes), education, and art among others in relaxing or exciting environments.

Participants may receive one of these two catalogues to complete over the course of their participation, regardless of study group assignment.

Each session will be supervised by a study technician trained to troubleshoot any problems related to the VR system, computer, games, or participants' intolerance of VR. All

sessions will be completed at the NYU Ambulatory Care Center.

6.1.2 Procedures for Training of Clinicians on Device

Formal training for study technicians will focus on familiarity with the computer and VR system and ensuring participant safety.

7 Study Procedures and Schedule

7.1 Study Procedures/Evaluations

Participants will complete an informed consent form before any study procedures begin. Participants under the age of 18 will complete an assent form while their legal parent or guardian will complete a consent form.

Participants will complete relevant assessments listed in [Table 2](#) before undergoing a VR session.

Participants may complete as much as one hour of VR therapy during any given session.

Study Group 1: There may be as many as twelve VR sessions during the course of the study. Study personnel will be available to guide participants during the entire duration of the VR session and ensure each session is completed safely. VR treatment will entail use of computer software designed to immerse participants and engage them in exercises. Software includes virtual painting, walking through vivid and calming settings, solving puzzles, among others.

Study Group 2: Similar to study group 1, study personnel will be available to guide participants throughout each VR session. VR treatment will be identical to study group 1.

Participants with MS will only be able to receive eight treatment sessions in this study group and will complete their treatment over four weeks.

Two treatments sessions must be completed each week (of the four weeks) and separated by at least one day. For example, if a participant completes one of their weekly treatments on Monday, they are not able to complete the treatment on Tuesday but may come in on any of the remaining weekdays that study staff are available.

Participants will attend a baseline visit with assessment and training procedures and receive their first treatment immediately after all baseline assessments. Participants will then complete the remaining seven treatment sessions over four weeks. At the final treatment session, participants will repeat assessments. One week following the final treatment session, participants will be asked to return to clinic to complete assessments once more to test cumulative benefits one week following treatment end.

CONFIDENTIAL

This material is the property of the NYU School of Medicine and Langone Medical Center. Do not disclose or use except as authorized in writing by the study sponsor

7.2 Study Outcome Measures

Table 3 below lists all outcome measures and time points at which they will be completed.

Measure	Screening***	Baseline/First Session	Follow-up/Treatment Sessions	Final Visit
Symbol Digits Modalities Test (SDMT)	X	X	X**	X
Wide Range Achievement Test (WRAT-4)	X			
VR Tolerability and Competence Test	X	X		
VR Session Questionnaire		X	X	
Pre and Post VR Session Evaluation		X	X	
Baseline VR Experience Questionnaire		X		
Study End VR Experience Questionnaire				X
Neuro-Quality of Life Questionnaires*		X	X	X
PROMIS Measure of Fatigue, Mood and Health Related Quality of Life**		X	X	X
Fatigue Severity Scale*		X	X	X
Beck Depression Inventory*		X	X	X
Positive and Negative Affect Schedule**		X	X	X
Rey Auditory Verbal Learning Test*		X	X	X
Brief Visuospatial Memory Test - Revised*		X	X	X
King Devick Test*		X	X	X
Cogstate Brief Battery*		X	X	X
Grooved Pegboard*		X	X	X
Grip Strength*		X	X	X
Test of Everyday Cognitive Abilities*		X	X	X
Modified Fatigue Impact Scale*		X	X	X
Cognition Lab*		X	X	X
Pain Catastrophizing Scale**		X	X	X
Symptom Catastrophizing Scale**		X	X	X
Immersion Rating Scale*		X	X	X
Toronto Mindfulness Scale**		X	X	X
Spatial Positioning Recording*		X	X	X
Brief Pain Inventory**	X	X	X	X
Automatic Thoughts Questionnaire – 30 Item**		X	X	X
Wong-Baker Faces Pain Rating Scale**		X	X	X

*:Optional measures that may be excluded based on study personnel judgement. **: Optional for study group 1 but required for study group 2 (Chronic Pain in MS). *** Screening assessments may be used as the Baseline assessment if Screening and Baseline are within two weeks.
				

CONFIDENTIAL

This material is the property of the NYU School of Medicine and Langone Medical Center. Do not disclose or use except as authorized in writing by the study sponsor

8 Assessment of Safety

Per HTC Vive manufacturer's specifications, in-clinic participation will ensure the area around the patient is safe and with no obstructions. Immersive VR will be used under the supervision of the research assistant in charge of the session. Immersive VR may cause dizziness, nausea, or headache. **However, such adverse events are highly infrequent and we expect that the proposed treatment to be highly tolerated. This study poses minimal risk to participants.**

If discomfort is great enough that the participant wants to cease the session, the experiment will stop and symptoms should resolve after a brief rest. Additionally, this study poses no greater risk for children.

We will utilize operating procedures for reviewing patient safety data and source data generated from this study. If after the first 10 subjects the compliance or incidence of adverse events is poor, the study will be put on hold and reviewed. Safety is emphasized in our study protocol and risk is minimal in that there should be no harmful, long term side effects or adverse effects from the VR sessions.

An adverse event is defined as any experience that negatively affects the wellness of a participant that can reasonably be attributed to the effects of the VR treatment. Adverse events that are unexpected, harmful, and related to the VR will be reported to the IRB. Examples of adverse events that are expected include: dizziness, nausea, vertigo, headache, etc. The PI will evaluate and follow AEs and AEs that are not severe as determined by the PI will be submitted within 5 business days of the occurrence of the event.

Specific attention will be given to data quality and timeliness, HIPAA-compliant, safe storage of data, and data backup of electronic source data. Attention will also be given to participant recruitment, participant risk versus benefit, adverse events, and other factors that can affect study outcome, including scientific or therapeutic developments that may have an impact on the safety of the ethics of the study.

We will submit data safety monitoring reports to the IRB after 10 participants are enrolled, and follow with reports for each further increment of 10 active enrollees. The study PI will review data safety reports in order to assess whether AE incidence rate is on par with that in publisher literature[19]. The research coordinator will submit data safety monitoring reports reviewed and signed by the PI. Any adverse effects, such as feelings of nausea, will be catalogued and quantified to determine rates of incidence. If the rates of incidence are higher than previously expected by PI based on literature then the study will be placed on hold and assessed. The most common adverse event expected is motion sickness and nausea, of which estimates of incidence vary across studies as technology has advanced and varied greatly over the last 20 years (some studies report 97% of participants as reporting none to mild nausea[19]). We conservatively expect a 20% incidence rate for feelings of motion sickness or nausea. We also expect other adverse event incidence rates such as headache, vertigo, and seizures to be exceptionally low, below 5% of occurrence.

9 Statistical Considerations

Study Group 1: As this is an exploratory protocol that is collecting data for future power analyses, the designation of recruiting 60 human subjects is somewhat arbitrary. Following the results and any benefit experienced by these initial participants, future clinical trials can be conducted with properly powered samples. Recruitment of 60 participants would allow for enough data for a sufficient power calculation for future trials to determine clinical efficacy.

Preliminary paired sample t-tests will be conducted to determine whether participants experienced statistically significant change in neurological disorder symptoms.

General means and standard deviations will be reported and analyses will inform future power analyses of clinical trials that will use VR as a treatment modality.

Study Group 2: The second pool of participants will be n=44, following preliminary effect size analyses. Participants who complete at least 6 of the 8 (75%) total sessions will be included in analyses, and we have anticipated a dropout rate of up to 10%, resulting in 20 or more completers in each group.

CONFIDENTIAL

This material is the property of the NYU School of Medicine and Langone Medical Center. Do not disclose or use except as authorized in writing by the study sponsor

Primary outcome will be the change in PROMIS Pain interference from baseline to the study end visit. Based on a previous, successful clinical trial in chronic pain also using an 8-session nonpharmacologic intervention[20], we can expect to have 89% power to detect a significant group difference between the two study conditions. We will also compare change between the groups from baseline to treatment end on the additional self-report measures.

Secondary outcomes will be change in pain visual analog scales completed before and after each session to evaluate acute treatment effects and changes in medication usage from baseline to treatment end measured qualitatively[21]. We will also analyze pain before and after each VR session with the Wong-Baker Faces Pain Rating Scale to compare the immediate analgesic effects of each condition and this cumulative change across sessions.

10 Source Documents and Access to Source Data/Documents

Data will be entered in the HIPAA-compliant NYU REDCap database designed specifically for this study. An anonymous database number will be assigned to each participant and will be used for both the Data Entry Sheet and the Patient Follow-up Sheets. The original consent, which includes the patient name and ID number, will be stored separately in a locked filing cabinet in a locked office. Access to this data will be restricted to study personnel only. Research data will be entered online through the secure NYU database software REDCap and source documents will be kept in a locked filing cabinet in a locked office. Participant data will be coded by the assigned ID and identifying information will not be presented or published to maintain participant privacy and confidentiality.

11 Quality Assurance and Quality Control

- Development of standard protocols to perform all data collection and follow-up activities.
- Use of standardized forms.
- Uniform criteria for patient recruitment.
- Standardized data processing.
- Regular communications between study staff and study investigators to resolve questions.
- Performance monitoring of data collection and data processing activities, as well as preparation of periodic reports and analyses on performance monitoring.
- Monthly monitoring of recruitment statistics.

12 Ethics/Protection of Human Subjects

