12.4 PARTICIPANT AND DATA CONFIDENTIALITY19

CONFIDENTIAL

This material is the property of the NYU School of Medicine and Langone Medical Center. Do not disclose or use except as authorized in writing by the study sponsor

13	DATA HANDLING AND RECORD KEEPING	19
13.1	DATA COLLECTION AND MANAGEMENT RESPONSIBILITIES	19
13.2	STUDY RECORDS RETENTION.....	19
13.3	PROTOCOL DEVIATIONS	19
13.4	PUBLICATION AND DATA SHARING POLICY	20
14	STUDY FINANCES.....	20
14.1	COSTS TO THE PARTICIPANT	20
14.2	PARTICIPANT REIMBURSEMENTS OR PAYMENTS.....	20
15	CONFLICT OF INTEREST POLICY.....	20
16	ATTACHMENTS	21

CONFIDENTIAL

List of Abbreviations

AE	Adverse Event/Adverse Experience
HIPAA	Health Insurance Portability and Accountability Act
ICF	Informed Consent Form
IRB	Institutional Review Board
PI	Principal Investigator
VR	Virtual Reality
PwMS	People with Multiple Sclerosis

CONFIDENTIAL

Protocol Summary

[figure not shown]
Title	Virtual Reality (VR) to improve Quality of Life in Patients diagnosed with Neurological Disorders
Short Title	VR to improve Quality of Life
Brief Summary	Participants with neurological disorders will be recruited to complete sessions of virtual reality (VR) immersion. VR has been shown to have therapeutic benefit in certain patient populations and requires further clinical study to determine the extent to which VR can be used to rehabilitate and reduce symptom burden. This study seeks to pilot newly developed VR methods and collect preliminary data in order to support research grants and inform larger clinical trials. This proposed study will explore the tolerability and preliminary efficacy of Virtual Reality (VR), specifically to determine whether VR can acutely reduce the severity of symptom burden caused by neurological disorders. Additionally, a second group of MS participants with clinically significant pain will be recruited to test the analgesic effects of VR.
Phase	N/A
Objectives	Specific Aim 1: To test the feasibility and tolerability of immersive VR therapy in patients with neurological disorders. Specific Aim 2: To measure the efficacy of a VR program to manage chronic pain for people with multiple sclerosis.
Methodology	Study Group 1: Open-Label Study Group 2: Single blinded, randomized treatment allocation to one of two VR treatment conditions
Endpoint	Completion of up to twelve one-hour sessions of VR alongside study measures taken at the end of the last completed session

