2.4.2 Known Potential Benefits

Participants may experience benefit from this study such as improvement in their mood or physical sensations. Immersive VR therapy may reduce symptom severity experienced by those with neurological disorders.

3 Objectives and Purpose

Specific Aim 1: To test the feasibility and tolerability of immersive VR therapy in patients with neurological disorders.

The primary outcome will be the number of successfully completed VR sessions across all participants. Secondary outcomes will be the subjective assessment of tolerability and engagement. Participants will rate enjoyment, engagement, and any potential side effects of the VR therapy.

Specific Aim 2: To test the effects of immersive VR on symptom burden in patients with neurological disorders.

The primary outcome will be the change in dimensions of symptom burden in participants with neurological disorders. Universal symptom inventory measures (Patient Reported Outcomes Measurement Information System or PROMIS) will be administered before and after each session. A paired t-test will be used to determine whether the cohort has experienced statistically significant change following VR.

The secondary outcomes will include disease specific inventories (i.e. MFIS) which will be administered before and after each session and their change after VR will be evaluated.

CONFIDENTIAL

This material is the property of the NYU School of Medicine and Langone Medical Center. Do not disclose or use except as authorized in writing by the study sponsor

4 Study Design and Endpoints

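### PROMIS carries the Aim 2 primary outcome in Section 3 but is optional for Study Group 1 in Table 3, and the pair of scores for the paired t-test is not fixed

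*Combined protocol and SAP*

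**What the plan says.** Section 3, Specific Aim 2, concerns patients with neurological disorders: "The primary outcome will be the change in dimensions of symptom burden in participants with neurological disorders". Instrument and timing follow: "Universal symptom inventory measures (Patient Reported Outcomes Measurement Information System or PROMIS) will be administered before and after each session". So does the analysis: "A paired t-test will be used to determine whether the cohort has experienced statistically significant change following VR".

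Table 3 (Section 7.2) puts a double asterisk on the PROMIS row, and the footnote reads "Optional for study group 1 but required for study group 2". The footnote does not say who decides, or on what grounds. The row has one mark under each of three columns (baseline or first session, later sessions, final visit) and does not distinguish before from after. A separate row, "Pre and Post VR Session Evaluation", has no asterisk.

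Other sections describe the Group 1 analysis more loosely:
- The Statistical Analysis row of the Protocol Summary speaks of quality-of-life change between baseline and follow-up.
- Section 4.2.1 combines completing one session with change in baseline measures that it does not name.
- Section 9 plans preliminary paired t-tests for Group 1 without naming an instrument or time points.
- The Protocol Summary words the second aim differently from Section 3: "Specific Aim 2: To measure the efficacy of a VR program to manage chronic pain for people with multiple sclerosis".

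**The concern.** A primary outcome needs an instrument that is always collected and a contrast fixed in advance. Here one section requires the instrument and the schedule makes it optional. If collection is left to judgement, the participants with PROMIS data may differ from those without, for example in how well they tolerated the session or how burdened they were. The paired change would then describe a selected subset of the 60.

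The open choice of pair adds to this. A participant may have one session or twelve, so there may be one before/after pair or twelve, plus a baseline-to-final pair. A reader of the results could not tell which was planned as primary.

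Section 9 says that Group 1 means and standard deviations will feed later power calculations. A standard deviation of change is useful for that only if the instrument and interval behind it are known.

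**Working it through.** The plan gives no alpha, effect size, standard deviation or power for Group 1, and Section 9 calls the choice of 60 somewhat arbitrary. There is no stated figure to reproduce. The check is a comparison of sections.

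**1. Do the two statements concern the same people?** Yes. Aim 2 in Section 3 is about neurological disorders. Sections 5.4 and 5.6 use that label for Study Group 1, and Section 4.2.2 gives Group 2 its own primary endpoint. The optional label in Table 3 applies to Group 1.

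**2. How far apart are they?** Sections 4.1 and 5.5 allow 1 to 12 sessions.
- Section 3: 2 administrations × 1 session = 2, up to 2 × 12 = 24 per person, for all 60.
- Table 3: optional, so the number with any PROMIS change score can be anywhere from 0 to 60.

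**3. Does anything else restore the measure?**
- Section 5.5 repeats the baseline measures straight after session 1 if that is the last session. If PROMIS was left out at baseline, nothing requires it to be repeated.
- The unstarred before/after session form has the right timing, but no section says that it contains PROMIS or serves as the primary outcome.

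**4. Which pair is tested?**

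| Place | Contrast described | t-test named? |
|---|---|---|
| Section 3 | before and after each session; up to 12 pairs, none selected | yes |
| Section 9 | none given | yes |
| Protocol Summary, Statistical Analysis | baseline to follow-up | no |
| Section 4.2.1 | change in unnamed baseline measures | no |
| Section 5.5 | baseline to just after session 1, if that is the last session | no |

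Only Section 3 ties a t-test to timing, and it does not choose among the pairs. The others neither choose one nor agree on the kind of change.

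**5. Scale, for illustration only.** Assume two-sided alpha 0.05.
- If k pairs were each tested separately and the tests were independent, the chance of at least one false positive is 1 − 0.95^k: 9.75% for k = 2, 26.5% for k = 6 and 46.0% for k = 12. Repeated scores from the same people are correlated, so the real figures would be lower.
- If PROMIS were collected in only 45, 30 or 15 of the 60 (assumed counts), the standardized paired change detectable with 80% power (noncentral t) would rise from 0.37 to 0.43, 0.53 or 0.78.

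The inconsistency in steps 1 to 4 does not depend on these figures.

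**The case against.** Group 1 is exploratory, its t-tests are called preliminary, and nothing confirmatory rests on them. That stands, and it limits the severity. It does not reconcile Section 3 with Table 3.

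Several stronger readings are tempting but not supported:

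- **The synopsis sets a rival primary outcome for Group 1.** Its Aim 2 is the Group 2 aim, so the mismatch is in how the aims are worded. Its Endpoint row, "study measures taken at the end of the last completed session", is neither labelled primary nor assigned to Group 1. Section 4.2.1 can be read as a loose restatement of the two Section 3 primaries, session completion and symptom change.
- **The sections give conflicting definitions of the t-test.** Only Sections 3 and 9 name one, and Section 9 gives no pair. The pair is unspecified; it is not defined in two incompatible ways.
- **PROMIS can be skipped without any deviation.** Section 3 says that it will be given, so omitting it departs from Section 3 even though Table 3 permits it. The position is ambiguous.
- **Before/after symptom data may be missing altogether.** The session form is not optional. The measures are attachments held outside the protocol, so its content cannot be judged here.
- **The asterisk on the MFIS is the same defect.** Section 3 cites it as an example of "disease specific inventories (i.e. MFIS) which will be administered before and after each session". In a group open to any neurological disorder, an optional disease-specific scale is to be expected.
- **A future trial would be underpowered because standard deviations are pooled over mixed intervals.** Section 9 does not say they will be pooled, the effect disappears under the within-session reading of Section 3, and any figure would rest wholly on assumed correlations and shares. The nominal Group 1 duration is about 12 days; one year is an outer limit.

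**Conclusion.** The point holds in two parts. First, the only instrument named for the Aim 2 primary outcome is required by Section 3 and optional for Group 1 in Table 3, with no before/after timing there. Following Table 3 can leave it uncollected or selectively collected in any number of the 60 participants. Second, no section fixes which pair of scores the Aim 2 t-test uses.

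Both conclusions rest on the text alone, and confidence in them is high. How much data would actually be lost cannot be known from the documents. Given the declared pilot status, this is a change the plan should make, and no more than that.

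**What to change.** 1. Remove the double asterisk from the PROMIS row of Table 3, so that PROMIS is required in both groups, and show the before and after administrations. If giving it at every session is not intended, amend Section 3 and Table 3 together to the same required time points: at least before and after session 1 and at the final visit.
2. State one pair of time points for the Aim 2 paired t-test, in identical terms, in the Protocol Summary and Sections 3, 4.2.1 and 9. Before versus after session 1 is one workable choice, because everyone who completes session 1 can supply it. The documents do not dictate it.
3. Report means and standard deviations of within-session change and of baseline-to-final change separately, with number of sessions and elapsed time. The number of visits is at staff discretion and may extend over as much as a year (Sections 4.1 and 5.5), and these figures are meant for later power calculations.
4. Align the wording of Aim 2 in the Protocol Summary with Section 3.

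The cost is amendment wording, less freedom to skip the measure, and a questionnaire Section 3 already calls for. The reduced schedule needs three administrations per person, or two if session 1 is the last, against as many as 24 under Section 3 as it stands.

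### Attribution to VR is part of the adverse event definition, so recorded incidence and the hold rules may run low, and no reporting deadline is stated for severe events

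*Combined protocol and SAP*

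**What the plan says.** All of the relevant text is in Section 8 (Assessment of Safety).

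- **Definition.** An adverse event is an experience with a negative effect on the participant's wellness "that can reasonably be attributed to the effects of the VR treatment". The section does not say who makes the attribution. The PI evaluates and follows events and decides whether they are severe.
- **Reporting of individual events.** "Adverse events that are unexpected, harmful, and related to the VR will be reported to the IRB"; no time limit is given. A later sentence says that "AEs that are not severe as determined by the PI will be submitted within 5 business days of the occurrence of the event"; no recipient is named.
- **Periodic reports.** "We will submit data safety monitoring reports to the IRB after 10 participants are enrolled", and again for each further 10 active enrollees.
- **Counting.** "Any adverse effects, such as feelings of nausea, will be catalogued and quantified to determine rates of incidence".
- **Expected rates.** "We conservatively expect a 20% incidence rate for feelings of motion sickness or nausea". Headache, vertigo and seizures are each expected below 5%.
- **Hold rules.** The study is put on hold if adverse event incidence (or compliance) is poor after the first 10 participants, and also if incidence is higher than the PI expected from the literature. Neither rule has a numeric boundary.

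**The concern.** Two separate problems follow from this text.

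First, the definition joins two questions that are normally kept apart: whether something untoward happened, and whether VR caused it. Section 8 names dizziness, nausea, vertigo and headache as expected effects of VR and gives an expected rate for seizures. In people with neurological disorders, several of these can also come from the disease. That is my clinical inference, but Sections 5.1 and 5.2 exclude only uncontrolled epilepsy and a current diagnosis of vertigo, so the overlap is narrowed and not removed. An event put down to the disease does not meet the definition. The filter can only lower the count, and an event that was not recorded cannot be restored at analysis. The count is what both hold rules use.

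Second, the timing rule seems to be the wrong way round: the milder events carry a deadline and the severe ones carry none. The sentence may be a drafting slip, but it is the text that staff have to follow.

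**Working it through.** **No figure to reproduce.** No sample size, power or alpha figure depends on this point. The 20% and below-5% rates are stated expectations, not derived values.

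**How far attribution could move the hold rule (illustration).** Let *t* be the true proportion of participants affected and *a* the share of those events attributed to VR. Both are assumed, because the protocol gives neither. The recorded rate is *p* = *t* × *a*. As a working boundary, take a recorded count above the expected 20%: at least 3 of 10 at the first look, or at least 13 of 60 in Group 1 (20% of 60 is 12). This boundary is also mine.

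For 10 participants, P(X ≥ 3) = 1 − [(1−p)^10 + 10p(1−p)^9 + 45p²(1−p)^8].

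- *t* = 30%, *a* = 100%, *p* = 0.30: 1 − (0.028 + 0.121 + 0.233) = 0.617 before rounding of the terms.
- *t* = 30%, *a* = 50%, *p* = 0.15: 1 − (0.197 + 0.347 + 0.276) = 0.180.

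| True rate | Share attributed | Recorded rate | P(≥ 3 of 10) | P(≥ 13 of 60) |
|---|---|---|---|---|
| 30% | 100% | 30% | 0.617 | 0.943 |
| 30% | 90% | 27% | 0.534 | 0.860 |
| 30% | 75% | 22.5% | 0.398 | 0.611 |
| 30% | 50% | 15% | 0.180 | 0.106 |
| 40% | 100% | 40% | 0.833 | 0.999 |
| 40% | 50% | 20% | 0.322 | 0.424 |

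The true rate is set above 20% on purpose. At a true rate of exactly 20%, the probabilities at the first look are 0.322, 0.180 and 0.070 for attribution shares of 100%, 75% and 50%. A hold at that rate would be a false alarm, so the fall shows fewer false holds, not lost protection.

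One limit applies to the whole table. The 20% benchmark is for nausea or motion sickness, which during a headset session is less likely to be put down to the disease than headache, vertigo or a seizure. The table shows the mechanism and does not estimate the effect.

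**The two reporting sentences, by type of event** (all VR-related, since that is part of the definition):

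| Event | IRB sentence applies | 5-business-day sentence applies | Stated deadline |
|---|---|---|---|
| Not severe, expected | no | yes | 5 business days |
| Not severe, unexpected and harmful | yes | yes | 5 business days |
| Severe, unexpected and harmful | yes | no | none |
| Severe, expected | no | no | none |

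For the last row only the periodic report is left, and that is triggered by enrolment counts, not by time or severity.

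**The case against.** A reader might infer that tolerability itself is under-counted. The documents do not support that. The primary outcome of Specific Aim 1 (Section 3) is the number of completed sessions, and the secondary outcomes are rated by participants. The Group 1 secondary endpoint (Section 4.2.1) turns on any possible side effect. Table 3 in Section 7.2 lists a VR Session Questionnaire and a Pre and Post VR Session Evaluation, neither marked optional. None of these uses the Section 8 definition.

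A reader might also infer that unattributed events are never recorded. That is too strong. Section 8 promises that "Any adverse effects, such as feelings of nausea, will be catalogued and quantified to determine rates of incidence", Section 5.7 has the participant rate an event when a session is paused, and the attribution test is a permissive one. The offset is only partial: adverse effect is not defined, it is itself causal wording, and the questionnaires are not said to feed the counts or the hold rules.

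Nor do the documents say that unblinded staff make the attribution. No assessor is named. Group 1 has no comparator. In Group 2 blinding is stated for participants only, so attribution could differ between catalogues, but nothing shows that it would.

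Severe events are not left without any rule either: unexpected, harmful ones go to the IRB. What is missing is a time limit, and any individual report for severe expected events.

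The strongest objection concerns the remedy. Running the hold rule on all-cause events would compare background neurological symptoms with a VR-literature benchmark. If background headache were 20% (assumed), at least 1 of 10 participants, which already exceeds 5%, would have it with probability 1 − 0.8^10 = 0.89. This stands, and the fix below allows for it.

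**Conclusion.** The point holds in two parts. Adverse event incidence, and the hold rules that depend on it, may be under-counted because attribution to VR is a condition of being counted. The size cannot be derived from the documents: it is zero if every event is attributed to VR, and large if about half are (0.62 to 0.18 in the first 10, and 0.94 to 0.11 in 60, at an assumed true rate of 30% and an assumed boundary of more than 20%). Separately, and without any assumption, the written text gives no deadline for severe events and places a severe but expected event outside both reporting sentences. The conclusion does not extend to the session-completion or participant-rated outcomes. This should be changed, because events left out of the record cannot be recovered later.

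**What to change.** - Record every untoward event during participation regardless of cause, with relatedness and severity as separate fields and a named assessor.
- Report incidence for all events and for related events.
- Keep the comparison with the VR-literature rates on the related subset, including possibly related events, and show the all-event rate beside it.
- Reconcile the two reporting sentences in Section 8. The sponsor should state the recipient and the timing for severe events, including expected ones; what that timing should be is for the sponsor to decide.

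The cost is a few sentences in Section 8 and extra fields on the session form. Because participation can run for up to a year, events between sessions also have to be asked about at visits. The small downside is that more minor events are recorded and the reported rate is higher.
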